# 5.1.3. Data Safety Monitoring Board (DSMB)

An independent committee consisting of experts in malaria, pediatrics, statistics and other appropriate disciplines has been appointed to oversee ethical and safety aspects of the study conduct. A quorum of 3 members is required at scheduled meetings.

The role of the DSMB includes the review of the implementation and progress of the study. It provides initial, regular, and closing advice on safety-related issues to GSK Biologicals. Its advice is based on the interpretation of study data with reference to the study protocol.

The DSMB will confer before the initiation of the study (pre-initiation review), during the study at points of safety review and at the close of the study. They will review the Protocol, Report and Analysis Plan (RAP) and Study Report. Other unscheduled

meetings may be required. Meetings must be documented and minutes made available to the sponsors. The DSMB may, if deemed necessary, convene a meeting with, or request further information from the Principal Investigators, the Medical Monitor/Local Safety Monitor and GSK Biologicals' and MVI at PATH's designated project representatives at any stage of the study.

The DSMB is empowered to suspend the enrollment to the trial and/or vaccination on the trial pending review of potential safety issues; complete details of this process are given in Section 5.1.5.

#### 5.1.3.1. Data Reviewed by the DSMB

The DSMB must be informed by the Local Safety Monitor (LSM) of the following safety data on an 'as received' basis:

- All SAEs;
- All withdrawals of study subjects by the Principal Investigator or the parent(s)/guardian(s) of a subject due to adverse events.

The DSMB will receive from the sponsor, GSK Biologicals:

- Safety summary reports at 3 predefined timepoints; after 30, 60 and 100 subjects have been enrolled and have completed the first 7 days of follow-up post Dose 1 of RTS,S/AS02D or Engerix-B (refer to Section 5.1.5 for the contents of the summary reports).
- New information that may affect adversely the safety of the subjects or the conduct of the study;
- All subsequent protocol amendments, informed consent changes or revisions of other documents originally submitted for review;
- All subsequent protocol modifications (for information).

## 5.1.4. Local Safety Monitor (LSM)

The overall role of the Local Safety Monitor (LSM), who is an experienced clinician based in-country, will be to support the clinical investigators and to act as a link between the investigators and the DSMB.

The LSM's role will include:

- Acting as the study volunteer's advocate;
- Promptly communicating relevant safety information to the DSMB;
- Providing advice to the investigators on whether a set of clinical circumstances in a study warrants formal notification to the DSMB;
- Unblinding a subject if deemed necessary to allow for adequate treatment;
- Liaising closely with the chair of the DSMB throughout the course of the trial;

• Suspension of vaccination for a major safety concern pending discussion with the DSMB (see Section 5.1.5 for full details).

#### 5.1.4.1. Data Reviewed by the LSM

The LSM must be informed by the investigator on an 'as received' basis of:

- All SAEs;
- All withdrawals of study subjects by the Principal Investigator or the parent(s)/ guardian(s) of a subject due to adverse events.

## 5.1.5. Safety monitoring plan

Safety reports will be produced for the DSMB on all data collected until 3 points in the study; after 30, 60 and 100 subjects have been enrolled and have completed the first 7 days of follow-up post Dose 1 of RTS,S/AS02D or Engerix-B. An independent statistician will analyze the data, thereby maintaining the blind of the malaria project team at GSK Biologicals and the investigator group. If a criteria for the suspension of enrolment or vaccination (refer to Section 5.1.6.2 and Section 5.1.6.1 respectively) is met, or the DSMB have any safety concerns about the vaccines, they may suspend the ongoing enrollment and vaccination in the trial. The process outlined in Section 5.1.6 will be followed.

The reports will contain analyses by group:

- All SAEs and any relationship to vaccine (RTS,S/AS02D, Engerix-B or TETRActHib) to date
- For each dose of RTS,S/AS02D or Engerix-B and TETRActHib, all solicited AEs tabulated by severity grading (any and Grade 3 alone) and relationship to vaccine.
  - Should the investigator judge a case of Grade 3 fever to be unrelated to vaccination, an alternative explanation for the cause of the fever will be provided
- For each dose of RTS,S/AS02D or Engerix-B and TETRActHib, all unsolicited AEs tabulated by severity grading (any and grade 3 alone) and relationship
- All laboratory values up to 30 days post Dose 3 presented as number of subjects out of range (above and below normal range) at each sampling time point (post doses 1 and 3 of RTS,S/AS02D or Engerix-B)
- Laboratory values are scheduled to be collected at 1 week post Dose 1 of RTS,S/AS02D, 1 month post Dose 3 of RTS,S/AS02D, 5/2 months post Dose 3 of RTS,S/AS02D and at the end of the single-blind phase of the study (Month 14). All available laboratory values up until the data base lock point of each of the three scheduled safety reports will be provided (Amended 29 June 2005)
  - For all subjects out of range clinical details will be provided
- All withdrawals of study subjects by the Principal Investigator due to adverse events recorded from the infants or withdrawals of infants by the parent(s)/guardian(s)

following doses of RTS,S/AS02D or Engerix-B and TETRActHib (expressed as percentage of subjects enrolled).

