age: in Cohort 2 related fever was observed after 4.9% of doses in children < 24 months, 1.3% of doses in children  $\ge$  24 months). In recipients of control vaccines in Cohort 1, fever was also the most commonly observed solicited adverse event related to vaccination (1.1% in children < 24 months of age [who received Prevnar and Hiberix] and 0.9% in children > 24 months of age [who received Engerix-B]). For recipients of RTS,S/AS02A < 24 months of age, a trend of increased local reactogenicity with sequential doses was observed. For recipients of RTS,S/AS02A  $\ge$  24 months of age, local reactogenicity was most frequent following Dose 3. The incidence of general symptoms of drowsiness, irritability, loss of appetite and fever ( $\ge$  37.5°C) was higher in recipients of RTS,S/AS02A than recipients of control vaccine; Grade 3 events were infrequent. In children < 24 months, the most commonly reported AEs were Upper Respiratory Tract infection, Malaria and Diarrhea and in children  $\ge$  24 months Upper Respiratory Tract Infection (URTI), Malaria and Ascariasis; frequencies were similar in the RTS,S/AS02A and control groups.

Dose								CO	HORT	1 All	/Dose						
Group			R(1	)<24			C(1)	)<24			R(1)	>24			C(1)	>24	
N			5	58			55	51			17	58		1768			
		n	%	95%	6 CI	n	%	95%	% CI	n	%	95%	6 CI	n	%	95%	6 CI
				LL	UL			LL	UL			LL	UL			LL	UL
Pain	Any	165	29.6	25.8	33.5	43	7.8	5.7	10.4	459	26.0	23.9	28.1	78	4.4	3.5	5.5
	Grade 3	2	0.4	0.0	1.3	0	0.0	0.0	0.7	3	0.2	0.0	0.5	1	0.1	0.0	0.3
Swelling	Any	133	23.8	20.4	27.6	54	9.8	7.4	12.6	314	17.8	16.0	19.6	54	3.1	2.3	4.0
	Grade 3	45	8.1	5.9	10.6	8	1.5	0.6	2.8	104	5.9	4.8	7.1	1	0.1	0.0	0.3
Drowsiness	Any	38	6.8	4.9	9.2	15	2.7	1.5	4.5	46	2.6	1.9	3.5	25	1.4	0.9	2.1
	Grade 3	5	0.9	0.3	2.1	1	0.2	0.0	1.0	5	0.3	0.1	0.7	2	0.1	0.0	0.4
	Rel* Grade 3	0	0.0	0.0	0.7	0	0.0	0.0	0.7	0	0.0	0.0	0.2	0	0.0	0.0	0.2
Irritability	Any	73	13.1	10.4	16.2	14	2.5	1.4	4.2	53	3.0	2.3	3.9	22	1.2	0.8	1.9
	Grade 3	4	0.7	0.2	1.8	1	0.2	0.0	1.0	3	0.2	0.0	0.5	3	0.2	0.0	0.5
	Rel* Grade 3	0	0.0	0.0	0.7	0	0.0	0.0	0.7	0	0.0	0.0	0.2	0	0.0	0.0	0.2
Loss of	Any	101	18.1	15.0	21.6	33	6.0	4.2	8.3	130	7.4	6.2	8.7	62	3.5	2.7	4.5
Appetite	Grade 3	6	1.1	0.4	2.3	2	0.4	0.0	1.3	4	0.2	0.1	0.6	3	0.2	0.0	0.5
	Rel* Grade 3	0	0.0	0.0	0.7	0	0.0	0.0	0.7	0	0.0	0.0	0.2	0	0.0	0.0	0.2
Temperature	Any	152	27.2	23.6	31.1	32	5.8	4.0	8.1	173	9.8	8.4	11.3	91	5.1	4.2	6.3
	Grade 3	10	1.8	0.9	3.3	1	0.2	0.0	1.0	7	0.4	0.2	0.8	6	0.3	0.1	0.7

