### 1.4.1. Safety monitoring plan

This study is the first administration of RTS,S/AS02D to infants and therefore a detailed safety plan, overseen by a formally constituted Data Safety Monitoring Board (DSMB) operating under a charter, is implemented (the role of the DSMB is fully detailed in Section 5.1.3). The DSMB is empowered to temporarily suspend the trial on the basis of any safety concern or meeting predefined criteria for temporary suspension (Section 5.1.6).

The rate of enrolment is uncertain as it is dependent on the birth rate, and could range from 6 to 12 months. The DSMB will receive all SAEs within 24 hours. In addition, the DSMB will review summarized safety and reactogenicity data at protocol-defined timepoints, so that enrollment to the trial could be halted in a timely fashion if a safety issue was detected (refer to Section 5.1.5).

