#### 5.1.6. Process for the suspension of vaccination

#### 5.1.6.1. Indications for immediate suspension of all vaccination

Immediate suspension of all vaccination on the trial will take place if:

- The Principal Investigator suspends vaccination for any of the following SAEs pending review by the DSMB;
  - Death or life-threatening SAE which is judged to be related to the study vaccine;
  - Anaphylactic shock reaction in an enrolled subject following vaccination.
- The DSMB recommend suspension of all vaccination for any one SAE or pattern of SAEs. The DSMB will communicate their recommendation to the Principal Investigator who will enact it. The DSMB will notify the sponsors of their decision immediately;
- The DSMB recommend suspension of all vaccination following their review of the safety summary reports

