#### 5.1.6.2. Indications for suspension of enrolment to the trial

Enrolment to the trial will be suspended if:

- The DSMB review of a safety report shows ≥ 5% of subjects vaccinated with RTS,S/AS02D are withdrawn by the investigator for local or systemic reactogenicity in recipients of RTS,S/AS02D. In making their recommendation the DSMB will take into account the full clinical history of each withdrawn child.
- The DSMB review of a safety report shows ≥ 5% of doses followed by fever > 39.0°C judged to be related to vaccination in recipients of RTS,S/AS02D. In making their recommendation the DSMB will review the investigators assessment of relatedness of all Grade 3 fevers.
- The DSMB recommend suspension of enrollment following their review of a safety summary reports.

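### The two 5% enrolment-suspension rules have no scheduled reading after the third DSMB report, with about 44–49% of infants still to be enrolled and most third doses still to be followed up

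*Protocol*

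**What the plan says.** Protocol 5.1.5 fixes the calendar. "Safety reports will be produced for the DSMB on all data collected until 3 points in the study": these are "after 30, 60 and 100 subjects have been enrolled and have completed the first 7 days of follow-up post Dose 1" of RTS,S/AS02D or Engerix-B. Sections 3 and 5.1.3.1 repeat the three points. Each report is by group, covers every dose given so far, and is prepared by an independent statistician.

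Protocol 5.1.6.2 gives two numerical rules that suspend enrolment:

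- "The DSMB review of a safety report shows ≥ 5% of subjects vaccinated with RTS,S/AS02D are withdrawn by the investigator" for reactogenicity.
- "The DSMB review of a safety report shows ≥ 5% of doses followed by fever > 39.0°C judged to be related to vaccination" in RTS,S/AS02D recipients.

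Both are conditional on what the review of a report shows. The section also lets the DSMB recommend suspension on its own judgement after reviewing a report.

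Protocol 5.1.6.1 works differently. It suspends vaccination for events such as "Death or life-threatening SAE which is judged to be related to the study vaccine", for anaphylactic shock, or on a DSMB recommendation about any SAE or pattern of SAEs. The SAE-based triggers wait for no report.

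Protocol 1.4.1 gives the purpose of the scheduled reviews: "so that enrollment to the trial could be halted in a timely fashion if a safety issue was detected".

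**The concern.** The numerical rules depend on a report, and the reports stop when 100 of 220 infants have a week of follow-up after Dose 1. No later scheduled DSMB report is described. The Visit 10 interim analysis (1.7, 10.8) serves sponsor and MVI development staff and is not described as a DSMB review.

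Between and after reports, the DSMB is sent SAEs and withdrawals for adverse events as they arrive (5.1.3.1). The Local Safety Monitor receives the same two items (5.1.4.1). A related fever above 39.0°C that is neither serious nor a cause of withdrawal is in neither list. The fever rule also needs a percentage of all RTS,S/AS02D doses, which means a by-group table, and only the three reports supply one.

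This is the first use of RTS,S/AS02D in infants, and safety is the primary objective. If related high fever became more frequent in later infants or at later doses, nothing scheduled would show the DSMB that 5% had been reached.

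**Working it through.** **Inputs.**

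- 220 infants, 110 per group (4.2).
- Doses on Days 14, 44 and 74 (5.4).
- Seven-day follow-up is the day of vaccination plus 6 days (10.2.1), so Dose 1 follow-up ends on Day 20.
- Enrolment takes 6 to 12 months (1.4.1). Section 10.5 gives 30 births a month with 25% ineligible.

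**The plan's own figures.** 110 × 3 = 330 RTS,S/AS02D doses, as in Appendix G. 220 / (30 × 0.75) = 9.8 months, inside the stated 6 to 12.

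**Assumptions.** Even enrolment, visits on schedule, no dropout, no lag to database lock. With 30.44 days a month, the daily rate is r = 220 / (months × 30.44): 1.205 at 6 months, 0.739 at 9.8 and 0.602 at 12.

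**Position at the third report.** The cut is 20 days after infant 100 enrols.

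- Enrolled by then = 100 + 20r.
- Follow-up complete after Dose 1 = 100, after Dose 2 = 100 − 30r, after Dose 3 = 100 − 60r.
- RTS,S/AS02D doses covered = half of the three counts added together.

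| Enrolment | Enrolled at cut | Still to enrol | Dose 1/2/3 complete, both groups | RTS,S/AS02D doses covered | Doses not covered | Third doses not covered |
|---|---|---|---|---|---|---|
| 6 months | 124 | 96 (44%) | 100/63/27 | 95 of 330 | 71% | 193/220 = 88% |
| 9.8 months | 114 | 106 (48%) | 100/77/55 | 116 of 330 | 65% | 165/220 = 75% |
| 12 months | 112 | 108 (49%) | 100/81/63 | 122 of 330 | 63% | 157/220 = 71% |

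Counting doses merely given by the cut, 61–68% of all doses and 70–85% of third doses are not covered. With 6-month enrolment, the 30- and 60-infant reports contain no third doses at all.

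**How much of this could still affect enrolment.** When the last infant enrols, follow-up is incomplete for infants enrolled in the last 20, 50 and 80 days (Doses 1, 2 and 3). That is 150r of 660 doses: 181 (27%) at 6 months and 90 (14%) at 12. For third doses it is 80r of 220: 96 (44%) and 48 (22%). Subtracting, 71 − 27 = 44% to 63 − 14 = 49% of doses complete follow-up between the last report and the close of enrolment. Those are the doses for which a reading could still act.

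**Timing of a single later report.** If it waits for infant 100 to pass 7 days after Dose 3 (Day 81), enrolment then stands at 100 + 81r: 198 (90%) at 6 months and 149 (68%) at 12. Ending on Day 80, as in the convention above, gives 89% and 67%.

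**The case against.** **Other safeguards continue.** A reader might infer that all suspension triggers lapse after 100 infants. The document does not support that. The SAE-based triggers of 5.1.6.1 cover every dose in every infant. SAEs reach the DSMB within 24 hours, and withdrawals for adverse events as received, so the withdrawal count is visible between reports. The Local Safety Monitor may suspend vaccination and passes on relevant safety information (5.1.4). The DSMB may meet unscheduled and request data (5.1.3). Grade 3 general symptoms found by field workers bring the child to a study clinician (5.1.12). All of this stands and narrows the gap to the fever percentage. None of it schedules that percentage for the DSMB.

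**Share of enrolment remaining.** The figure 100 of 220 invites the reading that more than half of enrolment is still to come. It is just under half, because enrolment continues during the 20 days to the cut.

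**Weight of Dose 1.** A reader might also infer that the rules are tested on the dose least likely to show trouble, since "a trend of increased local reactogenicity with sequential doses was observed" in children under 24 months (Malaria-026). That statement concerns local reactions. For related general events Malaria-025 found no rise with dose (1.3.3.2), and in Malaria-034, which used RTS,S/AS02D, symptoms became less frequent (1.3.3.4). The reports also include all doses to date. Dose 1 makes up 100/190 = 53% to 100/244 = 41% of the doses in the third report.

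**Yardstick.** Both rules suspend enrolment, so they have nothing to act on once it closes. That is correct, and the 63–71% should be read with it.

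**Design choice.** Concentrating reviews early is defensible in a first study in infants, and the DSMB charter, which is not shown, may provide for later meetings. Section 1.4.1 promises review at defined timepoints and 5.1.5 supplies them, so there is no strict contradiction. The point is that the calendar falls short of its stated purpose.

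**Conclusion.** The concern holds for the two 5% enrolment rules in 5.1.6.2, and chiefly for the fever rule. After the third report they have no scheduled reading, while 96–108 infants (44–49%) are still to be enrolled. About 63–71% of RTS,S/AS02D doses and 71–88% of third doses are never formally compared with them. Some 44–49% of all doses complete follow-up while enrolment is still open, so a reading could have had effect.

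These ranges rest on even enrolment over 6 to 12 months, on-time visits, no dropout and no database lag. Uneven enrolment would move the figures. The absence of a scheduled reading after the third report does not depend on these assumptions.

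The document does not support saying that safety oversight ends at 100 infants, or that the rules are tested on the wrong dose. This is an inexpensive improvement to the monitoring schedule; the thresholds are not at issue.

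**What to change.** Reconcile 1.4.1, 5.1.5 and 5.1.6.2 so that the scheduled readings match the stated aim. Leave both thresholds and the three reports as they are. Add that, after the third report, the independent statistician sends the DSMB the same two percentages, by dose and on all data to date, at set data transfers until enrolment closes. On the assumptions above, readings up to that close would cover about 73–86% of doses (100 − 27 to 100 − 14), against 29–37% now. Continuing until the last RTS,S/AS02D dose has been followed up is optional and would cover them all. Any decision stays with the DSMB.

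One extra report timed by the 100th infant's third dose is not enough, because about 68–90% of infants would already be enrolled.

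The cost is a few more runs of an existing table, some data cleaning and some DSMB time. The sponsor's project team and the investigators stay blinded, because the independent statistician does the work.

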#### 5.1.6. Process for the suspension of vaccination

#### 5.1.6.1. Indications for immediate suspension of all vaccination

Immediate suspension of all vaccination on the trial will take place if:

- The Principal Investigator suspends vaccination for any of the following SAEs pending review by the DSMB;
  - Death or life-threatening SAE which is judged to be related to the study vaccine;
  - Anaphylactic shock reaction in an enrolled subject following vaccination.
- The DSMB recommend suspension of all vaccination for any one SAE or pattern of SAEs. The DSMB will communicate their recommendation to the Principal Investigator who will enact it. The DSMB will notify the sponsors of their decision immediately;
- The DSMB recommend suspension of all vaccination following their review of the safety summary reports

#### 5.1.6.2. Indications for suspension of enrolment to the trial

Enrolment to the trial will be suspended if:

- The DSMB review of a safety report shows ≥ 5% of subjects vaccinated with RTS,S/AS02D are withdrawn by the investigator for local or systemic reactogenicity in recipients of RTS,S/AS02D. In making their recommendation the DSMB will take into account the full clinical history of each withdrawn child.
- The DSMB review of a safety report shows ≥ 5% of doses followed by fever > 39.0°C judged to be related to vaccination in recipients of RTS,S/AS02D. In making their recommendation the DSMB will review the investigators assessment of relatedness of all Grade 3 fevers.
- The DSMB recommend suspension of enrollment following their review of a safety summary reports.

#### 5.1.6.3. Process if the trial is suspended

Although the trial may be suspended by the DSMB, the LSM or the Principal Investigator, it is the responsibility of the sponsor (GSK Biologicals) to make the recommendation whether or not the trial should be stopped permanently.

If the trial is suspended, the DSMB will review all available information and make a recommendation to the study sponsor (GSK Biologicals) whether to recommence the trial or to stop the trial permanently. In the event that the DSMB recommend to stop the trial permanently, the FDA will be informed by GSK Biologicals that the trial is suspended.

In the event that the trial is suspended on the recommendation of the DSMB the sponsor (GSK Biologicals) will evaluate the information. If the sponsor concurs with the DSMB's recommendation to suspend the trial, GSK Biologicals will inform the FDA that the trial has been stopped permanently *temporarily*. If the sponsor's recommendation is to continue, then a report will be submitted to the FDA detailing the rationale used in reaching this decision. The agreement of the FDA will be obtained prior to restarting the trial (*Amended 29 June 2005*).

# 5.1.7. Completion of immunization course for infants withdrawn during vaccination course

Infants may be withdrawn by the investigator for medical reasons or by their parent(s)/guardian(s) for any reason. If there is no contraindication, in the opinion of the Principal Investigator, for the infant receiving additional doses of licensed vaccine for D, T, Pw, Hib and hepatitis B, the importance of completion of a 3 dose regimen will be explained to the parent(s)/guardian(s). The parent(s)/guardian(s) will be offered the choice of completing a course of TETRActHib + Engerix-B administered by the study team or completing a course of D, T, Pw, hepatitis B at their local EPI clinic.

#### 5.1.8. Rescue plan for Hepatitis B response

Antibody response to HBsAg will be determined 30 days after Dose 3 of RTS,S/AS02D or Engerix-B in infants. Infants who have not attained seroprotective levels of anti-HBs antibodies will be investigated further and their HBsAg measured to determine whether or not they are chronic carriers of hepatitis B virus. Chronic carriers are known to respond poorly to licensed hepatitis B vaccines and therefore may not benefit from additional doses of hepatitis B vaccine. Children who are not chronic carriers will be offered additional doses of the licensed vaccine. Children who are withdrawn, or drop out prior to the Day 104 will be invited to the Day 104 clinic visit (Clinic Visit 10) for safety monitoring and to assess their hepatitis B seroprotection status.

#### 5.1.9. Rescue plan for D, T, Pw, and Hib responses

The EPI vaccines are not coadministered with RTS,S/AS02D in this trial, but the third dose of TETRActHib will coincide with the administration of sulfadoxine-pyrimethamine (SP)and Amodiaquine for parasite clearance. Experience of the safety and immunogenicity of these drugs coadministered with EPI vaccines has been gathered in the evaluation of the malaria control strategy, the intermittent preventive treatment of infants IPTi [Schellenberg, 2001]. In this study, all infants will be monitored for their response to D, T, Pw and Hib and receive booster doses where required.

